In our study, a factorial design with 2 design variables (Cesarean Delivery Method [Gentle, Traditional] and Preference of Method [Gentle, Traditional]) will be used. A sample size of 508 total patients (127 patients in each of the 4 Method x Preference combinations) has been determined necessary to detect a 0.5-point difference in mean satisfaction scores (on a 5-point scale) and a 15-minute difference in time-to-initiation of family bond between the 2 groups of each design variable, given 2-factor generalized linear modeling with normally-distributed (or log-transformed) responses, standard deviation of 2 points (for satisfaction score) and 1-hour (for family bond initiation), alpha of 0.05, and power of 0.80. Moreover, to detect a 15% difference in probability of breastfeeding prior to discharge between the 2 groups of each design variable using logistic regression, a sample size of 432 total patients (108 patients in each of the 4 Method x Preference combinations) would be necessary. To detect clinically-relevant differences for all outcomes (responses) of interest in the Primary and Secondary Objectives, we will target 508 total patients.

VI. DESCRIPTION OF DELIVERY METHODS

Method 1: Family-centered cesarean

Standard preoperative preparation will be performed in the patient's room, including surgical site hair clipping, chlorhexidine wash (at ASMC only), IV placement, completion of pre-procedure operating room checklist, and administration of prophylactic antibiotics, antiemetics (at ASMC only), and fluids. The patient will then be taken to the operating room. The pulse oximeter will be placed on the mother, and the electrocardiogram leads will be placed away from anterior chest wall or via an EKG back-patch to allow space for newborn and mom skin contact. Regional spinal anesthesia will be administered in normal fashion. The mother will lie down on the bed and, once sufficient anesthesia block is obtained, her gown will be removed and a blanket will be provided for her to cover her chest, allowing for easier skin-to-skin contact after delivery. Prior to the lowering of the drape, the mother's head will be elevated. Fetal heart tracing will be monitored until adequate block is obtained to confirm fetal well-being.

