While on the mother's chest, the newborn's well-being will be initially evaluated by the nurse and respiratory therapist per hospital cesarean section protocol. APGAR scores will be obtained, and the pulse oximeter will be applied to the newborn's right hand. Suctioning needed at that time will be performed using a bulb or mechanical suction. The nurse will remain near the patient's head, as long as needed to ensure maternal and neonatal well-being. Should the mother develop complications that prevent her from being able to comfortably hold the newborn, such as nausea/vomiting, fatigue, or drowsiness from medications, the nurse will be available to help with the newborn. As long as the patient remains stable, the newborn will be laid on mother's chest in a way that allows suckling. The newborn vitamin K administration and erythromycin ointment can be applied per hospital protocol, either while she is holding the newborn or after she is in recovery. The newborn will be weighed following surgery, while the mother is transferred to her bed, unless she requests it be done earlier.

Method 2: Traditional cesarean

Standard preoperative preparation will be performed in the patient's room, including surgical site hair clipping, chlorhexidine wash (at ASMC only), IV placement, completion of pre-procedure operating room checklist, and administration of prophylactic antibiotics, antiemetics (at ASMC only), and fluids. The patient will then be taken to the operating room. The pulse oximeter will be placed on the mother's finger, and electrocardiogram leads will be placed in the usual fashion on the chest. Regional spinal anesthesia will be administered in normal fashion. The mother will lie down on the bed, and fetal heart tracing will be monitored until adequate block is obtained to confirm fetal well-being.

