Preoperative preparation will continue with abdomen preparation. We will then wait 3 minutes from wash to dry before placing the blue drape on the mother's abdomen and attaching it to the IV poles, thereby screening the mother from the entire surgery. After delivery, the newborn will be handed off to a nurse waiting at the side of the mother who will take the newborn to the warmer on the opposite side of the operating room. The newborn will be dried and warmed with fresh towels on the warmer, while being evaluated by the nurse and respiratory therapist per hospital cesarean section protocol. The nurse will then proceed with newborn measurements, weight, bath, and administration of vitamin K and erythromycin ointment. The newborn will be swaddled and kept in the warmer until the mom requests that the newborn be brought to her or until the surgery has been completed and the mom is ready to be transferred to the recovery room.

VII. DATA COLLECTION

Patients will be followed throughout their hospital stay. The following variables of interest will be retrospectively collected from EPIC or recorded during the surgery on the OR Worksheet (* - Note, the OR Worksheet was updated on 2/16/2018.):

Maternal Variables of Interest

- Medical record number
- Date of birth
- Delivery Hospital (0=ASMC; 1=ABMC)
- Date of consent for scheduled cesarean section
- Date of procedure
- Calculated maternal age
- Race
- Ethnicity
- Gravidity (Gx)
- Parity (Pxxxx)
- Gestational Age (XwXd)
- Height (inches)
- Weight (lbs)
- Calculated BMI (kg/m²)
- History of previous vaginal delivery (0=No; 1=Yes)
- History of previous cesarean delivery (0=No; 1=Yes)
- Reason for previous cesarean delivery
- History of previous abdominal/pelvic surgery (0=No; 1=Yes)
- Reason for planned cesarean delivery
- Type of cesarean delivery technique (0=Family-centered; 1=Traditional)
- Identified mother preference (0=Family-centered; 1=Traditional)
- Type of cesarean delivery (0=NA; 1=Classical; 2=Low Transverse)
- Type of skin incision (0=NA; 1=Pfannenstiel; 2=vertical)
- Operative start time (00:00:00)
- Operative stop time (00:00:00)
- Duration of operation (minutes)
- Estimated blood loss (mL)
- Hemorrhage EBL >1000mL (0=No; 1=Yes)
- Complications occurred (0=No; 1=Yes)
- Type(s) of complication(s) that occurred
- If the mother's delivery technique was family-centered, was she switched to a traditional cesarean? (0=No; 1=Yes)*
- Was mom offered to view the birth of her baby? (0=No; 1=Yes)*

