For each outcome of interest, we will also develop a mixed regression model to examine the fixed main and interaction effects of Method and Preference. All models will be structured with appropriate response distributions, likely including the lognormal (normal distribution with natural log-transformed response) for continuous responses (e.g., time, weight, vitals), multinomial for survey questions of satisfaction, and binomial for 2-category outcomes (e.g., breastfeeding). Following back-transformation or exponentiation of parameter estimates, model results will be interpreted, respectively, as the percentage difference between groups, ratio of odds of a lower value, and ratio of odds of an outcome occurring. Unobserved outcome heterogeneity will be captured by the delivering physician nested within hospital, each combination of which will define a separate random variable and model intercept.

IX. POTENTIAL RISKS AND BENEFITS

Risks associated with Method 1 (family-centered cesarean delivery) include unforeseen patient and/or family discomfort with viewing the surgical field. Patients will be made aware of the potential risk of such discomfort prior to consenting to participating in the study. Notably, risks of this nature are a normal component of any cesarean delivery. Therefore, we will discuss the risk of viewing discomfort with all patients regardless of study participation. An additional risk associated with participating in either method could be loss of confidentiality due to obtaining limited protected health information. However, to minimize risk, all data will be stored on a password protected computer.

A potential benefit of our study is that we may be able gather level-1 evidence to support local, regional, and possibly broader use of a novel method of cesarean delivery, currently being explored nationally and internationally. We hypothesize that there will be improved maternal satisfaction using the family-centered method. We also hypothesize that neonatal morbidity will not be increased and benefits may include earlier skin-skin contact and greater likelihood of breastfeeding.

X. REFERENCES

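### The outcome models include no baseline covariate and no fixed hospital term, which forgoes a modest power gain for Method and leaves the self-declared Preference main effect open to confounding

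*Combined protocol and SAP*

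**What the plan says.** Section VIII plans a mixed regression model for each outcome to "examine the fixed main and interaction effects of Method and Preference". The only other structure is the random part: "Unobserved outcome heterogeneity will be captured by the delivering physician nested within hospital", with one intercept per physician-hospital combination. Satisfaction items are modelled as multinomial, two-category outcomes such as breastfeeding as binomial, and continuous responses probably as lognormal.

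Section VII lists many maternal variables that are fixed before assignment, among them "History of previous cesarean delivery (0=No; 1=Yes" and "History of previous vaginal delivery (0=No; 1=Yes", together with parity, age, gestational age, BMI and delivery hospital. Section VIII uses patient characteristics to describe and test differences among the four Method-by-Preference cells. It does not carry them into the outcome models. The one mention of adjustment, at the end of the variable lists in Section VII, concerns women with an incomplete OR worksheet or survey.

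Under Section III, the woman states her preference after enrolment and before she is randomised to a Method. Section V nevertheless powers the comparison between the two groups of each factor, Preference included, to "detect a 0.5-point difference in mean satisfaction scores (on a 5-point scale) and a 15-minute difference in time-to-initiation of family bond", with "standard deviation of 2 points (for satisfaction score) and 1-hour (for family bond initiation), alpha of 0.05, and power of 0.80". Section VI shows that routine care differs by hospital in some respects, for instance "administration of prophylactic antibiotics, antiemetics (at ASMC only), and fluids", in the same way under both Methods.

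**The concern.** Two separate things are at stake.

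For Method, adjusting for baseline variables that predict the outcome uses data already collected to gain power and to offset chance imbalance. Section III describes a 1:1 set of envelopes with no stratification by hospital or birth history. Section V adds no allowance for dropout to a sample size that sits almost exactly at 80% power. The plan therefore has little reserve.

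For Preference, nothing has been randomised. Women with different birth histories, or at different hospitals, may prefer different methods and may also differ in satisfaction or breastfeeding for reasons unrelated to preference. A main effect from the planned model mixes these. Calling the design factorial and powering both factors alike invites readers to give the Preference result the same standing as the Method result.

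The physician-within-hospital intercept carries the hospital difference only in part. A random intercept shrinks a systematic difference between two sites towards zero, and some of it can remain in the Preference estimate.

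**Working it through.** **Inputs from the plan (Section V).** N = 508, so 254 per level of each factor; difference 0.5 points with SD 2 (equivalently 15 minutes with SD 60); alpha 0.05; power 0.80. Sidedness is not stated; two-sided is used here, because one-sided would need only 396.

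**Reproducing 508.** n per level = 2 × (1.96 + 0.84)² × SD² / difference² = 252 after rounding up, or 504 in total. At 254 per level, SE = 2 × √(2/254) = 0.1775, 0.5/0.1775 = 2.82, and power is 80.4% (80.3% with the noncentral t). The stated size is reproduced without covariates.

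**Method with covariates, linear scale.** If covariates explain a share R² of the outcome variance, the residual SD is 2 × √(1 − R²). The documents give no R², so these values are assumptions. Equivalent N is 508/(1 − R²).

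| Assumed R² | SE | Power at 508 | Equivalent unadjusted N |
|---|---|---|---|
| 0 | 0.178 | 80.4% | 508 |
| 0.05 | 0.173 | 82.4% | 535 |
| 0.10 | 0.168 | 84.4% | 564 |
| 0.20 | 0.159 | 88.3% | 635 |

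**Method with covariates, logistic scale.** The planned models for satisfaction and breastfeeding are not linear, so a binary outcome was simulated (1,500 runs, N = 508, true Method log-odds 0.55 given the covariate, one binary covariate).
- Covariate log-odds 1: power rose from 74.7% to 77.4% with adjustment.
- Covariate log-odds 2: power rose from 66.7% to 73.1%. The mean Method coefficient moved from 0.47 to 0.56, and its standard error rose from 0.199 to 0.217.

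The gain here is in power. The standard error does not shrink, and the odds ratio becomes conditional on the covariate. The multinomial model was not simulated; the same behaviour is expected there by analogy.

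**Preference: an omitted covariate.** Bias = covariate effect × difference in its prevalence between preference groups. Both factors are assumptions. False-positive rates use SE 0.1775 and assume equal preference groups.
- 0.5 points × 0.20 = 0.10 points; false-positive rate 8.7%.
- 1.0 point × 0.30 = 0.30 points; false-positive rate 39%.

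In the logistic simulation, with the covariate at 35% versus 65% across preference groups and no true Preference effect, the unadjusted Preference test rejected in 29% of runs (log-odds 1) and 77% (log-odds 2). With adjustment it rejected in about 5%.

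**Preference: hospital.** Assumptions: the share preferring one method is 35% at one hospital and 65% at the other, physician SD 0.3, residual SD 1.9, no true Preference effect, 1,500 runs of 508 women. Entries are the mean bias in the Preference effect, in points.

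| Hospital difference | Physicians per hospital | No hospital or physician term | Planned intercept | Intercept + fixed hospital |
|---|---|---|---|---|
| 0.5 | 5 | 0.150 | 0.053 | 0.000 |
| 0.5 | 10 | 0.153 | 0.080 | 0.001 |
| 0.5 | 20 | 0.145 | 0.099 | −0.006 |
| 1.0 | 5 | 0.302 | 0.059 | 0.002 |
| 1.0 | 10 | 0.302 | 0.100 | −0.001 |
| 1.0 | 20 | 0.297 | 0.148 | −0.004 |

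With the 1.0-point difference, false-positive rates were about 40%, 7 to 15%, and 5% across the three models. The Method standard error was 0.170 to 0.172 with the planned intercept and 0.169 to 0.170 with the fixed hospital term added, so hospital's precision gain is already captured. None of the simulated models included the Method-by-Preference interaction; they speak to main effects only.

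**The case against.** The case for leaving the plan alone has real weight.

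- Method is randomised, so leaving out covariates does not bias its comparison, and 508 delivers the stated power. A reader might infer that the primary analysis is biased or underpowered; the documents do not support that. This stands.
- A reader might infer that hospital is ignored. It is not: the random intercept is defined within hospital, removes part of any hospital confounding of Preference, and captures nearly all of the precision. Only the missing fixed term can be criticised.
- A reader might infer that the interaction is confounded too. Preference is recorded before assignment, so the interaction contrasts two randomised Method effects and is valid as such. What is not supported is the claim that preference itself causes the difference. Main-effect covariates would not repair that claim, which is a matter of interpretation.
- No figure in the documents shows that the recorded variables predict strongly. Gestational age in particular is restricted by the entry criteria to 38 weeks or more.
- No stated objective tests Preference, and the planned cell comparisons would make imbalance visible. But Section V powers Preference and Section VIII estimates its main effect, and seeing an imbalance does not remove it from the estimate.
- Section VIII speaks of developing models, which leaves room for covariates. With none named and interim analyses planned throughout, that freedom is a reason to fix the list.
- Adjustment for a few measured variables cannot remove unmeasured confounding. This stands, and it makes labelling Preference as observational at least as important as the covariates.

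**Conclusion.** The point holds as a modest improvement to the Method analysis and a real weakness in the Preference main effect. It does not invalidate the primary comparison.

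For Method, the forgone gain is about 2, 4 or 8 percentage points of power at assumed R² of 0.05, 0.10 or 0.20, on the linear scale. A reader might infer a loss of precision in every model. In the binomial models, and by analogy the multinomial ones, adjustment instead raises power and changes the odds ratio without reducing its standard error.

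For Preference, the illustrative bias of 0.10 points is a fifth of the 0.5-point difference that the trial is sized to detect (0.10/0.5). Its true size depends on covariate effects and prevalence gaps that the documents do not give. The planned intercept only partly removes confounding by hospital: in the simulated cases 0.05 to 0.15 points remained, against essentially none with a fixed hospital term.

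**What to change.** In Section VIII, before the final analysis:

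- Add a fixed hospital term and keep the physician random intercept.
- Add previous cesarean, previous vaginal delivery, maternal age and gestational age to all primary and secondary models, and add BMI for blood loss and operating time.
- Show the Method effect without covariates next to the adjusted one, and state that adjusted and unadjusted odds ratios estimate different quantities.
- Report the Preference main effect as an adjusted observational association. Describe the interaction as a difference in the Method effect between preference groups, with no causal attribution to preference.

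The change is to wording only, and every variable is already collected. It uses five degrees of freedom (hospital plus four covariates), or six with BMI, if each enters as a single term. The main downside is that the adjusted odds ratios are conditional and need that explanation when reported.

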To improve the overall child birthing experience, the family-centered/gentle cesarean delivery method mimics a vaginal birthing experience. Similar to a vaginal delivery, a mother can watch the birth, and the newborn is immediately placed on the mother's chest following cesarean delivery. Studies have shown that immediate mother-newborn interactions and skin-to-skin contact is advantageous in promoting the bond between mother and newborn, breastfeeding, and overall patient satisfaction with the birthing process.^{1, 5} The family-centered/gentle cesarean method is relatively new. Limited information is available in regards to differences in maternal and neonatal outcomes when comparing traditional cesarean methods to that of the family-centered/gentle cesarean. Additionally, available information often refers to this methodology as either family-centered cesarean or gentle cesarean; we will refer to this method as the family-centered cesarean from here on out.

One European study conducted in Germany compared family-centered and traditional cesarean delivery methods, and determined that no additional complications arose for mother or newborn when using the family-centered cesarean method.⁶ Although the Memorial Hospital of Rhode Island has implemented the family-centered cesarean method as the standard of care during cesarean delivery, to our knowledge, no studies have been conducted in the United States that compare the family-centered cesarean method to traditional methods of cesarean delivery.⁴ Magee et al. further supports that the techniques used in their hospital have not been evaluated and that the hospital's approach to family-centered cesarean deliveries should be further examined as it relates to maternal and neonatal outcomes, as well as overall patient satisfaction.⁴

The purpose of this study is to determine if patient birthing experiences differ between the family-centered and traditional cesarean methods. We hypothesize that the family-centered cesarean method will lead to more unique and personalized cesarean birthing experiences without increasing the risks of adverse neonatal and maternal outcomes from those documented

with the traditional cesarean.

II. SPECIFIC AIMS

Primary Objective

The primary objective of this study is to compare patient satisfaction of the family-centered cesarean birthing experience with that of the traditional cesarean experience.

Secondary Objective

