The secondary objective of this study is to determine if skin-to-skin contact (i.e., family bond initiation) occurs earlier and in-hospital breastfeeding initiation is more likely with the family-centered cesarean delivery method than traditional cesarean delivery method.

Tertiary Objective

The tertiary objective of this study is to determine if differences in maternal and neonatal outcomes exist between cesarean delivery methods (family-centered versus traditional cesarean).

III. STUDY DESIGN

Subject Enrollment

[figure not shown]
Women undergoing a scheduled cesarean delivery at ≥ 38 weeks of gestation who present at Aurora Sinai Medical Center and Aurora BayCare Medical Center and have their babies delivered by obstetrics and gynecology physicians during June 1, 2016 through May 31, 2019 will be enrolled in this study. Patients who meet the study criteria will be recruited via obstetrics and gynecology physicians on the day of their scheduled cesarean section. Patients who agree to participate in this study will be formally consented. The study will be described to the patient using the following script, containing objective language so as to minimize bias or influence when the patient is later asked to identify her preference of the 2 cesarean delivery methods. Note that Method 1 below describes the family-centered delivery method, while Method 2 describes the traditional delivery method.

“We are conducting a patient satisfaction study on two methods of cesarean section. Both of these methods are used throughout the United States, and neither has been proven to be better than the other. Method 1 involves lowering part of the surgical drape exposing a transparent window through which you can watch the birth of your baby; the baby will be placed on your chest immediately after the delivery. Cleaning and evaluation of your baby will be done by a nurse who is standing next to you at the head of the bed. Method 2 involves keeping the surgical drape up throughout the entire surgery so that the birthing process will not be visible, and your baby will be taken to the warmer to be evaluated and cleaned after birth but is available to be laid on your chest at any point upon request.”

Randomization to Method

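### For the four binary safety outcomes, the planned Method x Preference difference model cannot support the hypothesis of no increased risk and may not be estimable when events are few

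*Combined protocol and SAP*

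**What the plan says.** The hypothesis of no increase appears twice. Section I expects a better birthing experience "without increasing the risks of adverse neonatal and maternal outcomes from those documented" with the traditional method. Section IX adds: "We also hypothesize that neonatal morbidity will not be increased". The tertiary objective in section II is worded differently. It is to "determine if differences in maternal and neonatal outcomes exist between cesarean delivery methods".

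Section VII lists four yes/no outcomes that bear on the hypothesis: documented neonatal infection, surgical site infection, hemorrhage (estimated blood loss above 1000 mL) and any complication. It also lists measures that are not events, such as Apgar scores, 10-minute vital signs and time to oxygen saturation above 90%.

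Section VIII first plans descriptive summaries for all three objectives. Its inference is a single template: "For each outcome of interest, we will also develop a mixed regression model", with main and interaction effects of Method and Preference and random intercepts for physician within hospital. Two-category outcomes are reported as odds ratios. The section gives no between-arm risk difference with an interval, no margin or upper-limit criterion, and no fallback for sparse data.

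Section V sizes the trial on the primary and secondary outcomes only: "A sample size of 508 total patients (127 patients in each of the 4 Method x Preference combinations) has been determined necessary". No expected rate is given for any safety event.

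**The concern.** A claim of no increase is supported by an upper confidence limit that rules out increases large enough to matter. A model that looks for a difference does not supply this by returning a non-significant result, least of all when events are few and the interval is wide.

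The template also divides a small number of events among four cells. If one cell has no events, the interaction odds ratio is infinite or undefined under ordinary maximum likelihood, and so is the Method odds ratio within that preference group. Only Method is randomised. Preference is whatever each woman states, so the plan cannot guarantee equal cells. The random intercepts add further parameters to the same sparse data.

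At stake is the safety statement that will accompany the satisfaction result. Section IX hopes the trial will support wider use of the method, and as written the plan offers no sound way to say how large an increase in these events the data exclude.

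**Working it through.** **Inputs.** From section V: 508 in total, 127 per cell, hence 2 x 127 = 254 per Method arm; "alpha of 0.05, and power of 0.80". From section IV onward there is no event rate for any safety outcome, so 2%, 3% and 5% are assumptions. All 508 are taken as evaluable.

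**The plan's own figure.** The standardised effect is 0.5/2 = 15/60 = 0.25. The normal formula gives n = 2(1.96 + 0.8416)² / 0.25² = 251.2, so 252 per arm. The t-test version gives 253 per arm, or 506, which rounds up to 508 in four equal cells. Power at 254 per arm is 0.804. The 508 reproduces with a two-sided alpha and involves no safety outcome.

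**Power to detect a doubling from p to 2p.** Power = Φ((p − 1.96·se0)/se1), with se0 pooled and se1 unpooled. At p = 3%: se0 = √(2 × 0.045 × 0.955/254) = 0.01840 and se1 = √((0.03 × 0.97 + 0.06 × 0.94)/254) = 0.01835. Then (0.03 − 0.03605)/0.01835 = −0.330, and power is 0.37.

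**Upper 95% limit of the risk ratio when observed rates are equal.** Limit = exp(1.96·√(2(1 − p)/(254p))). At 3%: √(1.94/7.62) = 0.5046, and exp(0.989) = 2.69. Setting the limit to 2 gives 2(1 − p)/(254p) = (0.6931/1.96)² = 0.1251, so p = 2/(2 + 31.8) = 5.9%.

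**Chance of at least one cell without events.** With 127 per cell: 1 − (1 − (1 − r)^127)^4. With an assumed 85/15 preference split, each arm has cells of 216 and 38, and the product runs over those. At 5%, 0.95^38 = 0.142 and the large cells contribute almost nothing, so the chance is 1 − (1 − 0.142)² = 0.264.

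| Assumed rate | Expected events per arm | Power for a doubling | Upper risk-ratio limit, equal rates | Empty cell, 127 each | Empty cell, 216/38 |
|---|---|---|---|---|---|
| 2% | 5.1 | 0.26 | 3.4 | 27% | 72% |
| 3% | 7.6 | 0.37 | 2.7 | 8% | 53% |
| 5% | 12.7 | 0.57 | 2.1 | 0.6% | 26% |

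At 8% and 10%, power is 0.79 and 0.89 and the upper limit is 1.8 and 1.7.

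**Risk-difference scale.** The Wald half-width, 1.96·√(2p(1 − p)/254), is 2.43, 2.97 and 3.79 points at 2%, 3% and 5%. Against increases of 2, 3 and 5 points, it fails to exclude a doubling at 2%, is a near tie at 3%, and excludes it at 5%. At 3% the method matters: with 8/254 in each arm the Newcombe half-width is 3.3 points against 3.15 for a doubling, so a doubling stays inside.

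**Continuous outcomes, for contrast.** The half-width of a Method difference is 1.96·√(2/254) = 0.17 SD.

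**The case against.** The strongest reply is that safety is a tertiary objective, worded as a search for differences, and the planned model addresses that wording. Section VIII also promises descriptive summaries and expresses model results as odds ratios, which are estimates and not bare tests, and it leaves some latitude over response distributions. This stands as far as it goes. It does not meet the hypothesis in sections I and IX, and the descriptive part gives frequencies by cell, not an interval for the between-arm difference.

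A reader might infer four stronger things, none of which the documents support.

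- *That the whole safety assessment rests on rare events.* Apgar scores, vital signs, time to saturation, blood loss and operative duration are not rare events, and 254 per arm gives useful precision for the continuous measures.
- *That a doubling can never be excluded.* This depends on rates that the documents do not give. On the risk-ratio scale a doubling is excluded above about 6% if observed rates are equal, and hemorrhage or any complication might be that common. On the risk-difference scale the threshold is lower.
- *That the investigators will read non-significance as safety.* The plan nowhere says so. It leaves the reading open.
- *That the model will usually fail.* With 127 per cell the chance of an empty cell is 8% at 3% and under 1% at 5%. The larger figures need a preference split that is assumed here. An empty cell breaks the interaction terms, not necessarily an overall Method effect.

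**Conclusion.** The point holds for infrequent binary safety outcomes and no further. For documented neonatal infection, surgical site infection, blood loss above 1000 mL and complications, the stated analysis cannot support no increase. If rates are about 5% or lower, power to detect a doubling is at most 0.57, and identical observed rates would still leave a risk ratio of 2 inside the 95% interval. Below about 3% there is also a material chance that the interaction model cannot be estimated as written, and this extends to higher rates if stated preference is lopsided.

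These sizes rest on assumed event rates, on all 508 women being evaluable and, for the larger empty-cell figures, on an assumed 85/15 preference split. The primary and secondary analyses are untouched. The change is worth making because it is cheap and determines what the safety conclusion can say.

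**What to change.** In section VIII, name the four binary safety outcomes and make their main analysis a comparison by randomised Method alone. Report the risk difference with a two-sided 95% score interval (Newcombe or Miettinen-Nurminen) or an exact interval. Keep any Method x Preference odds-ratio model as supportive, fitted by penalised likelihood when a cell has no events.

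Add this sentence: *Absence of a significant difference will not be reported as no increase in risk; the conclusion will be the largest increase excluded by the upper confidence limit.*

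This needs no margin, extra patients or new data. The cost is a few lines of plan text and a more cautious safety statement. The main safety estimate would also no longer model physician-within-hospital heterogeneity, which the plan should acknowledge.
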